4.8.4 Not enough tissue left for imaging or removing a therapeutic shave

LUMICELL CONFIDENTIAL

This document is confidential. Do not disclose or use except as authorized.

This is a list of certain orientations in a given subject in which there is not enough tissue left for further imaging or removing a therapeutic shave. The margins of these orientations in the list will be ignored and will be treated as negative margin from the efficacy analyses.

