4.8.3 Missing and spurious data

During Luminicell-guided imaging, when there is not enough tissue to be removed (e.g. too close to skin or too close to the chest wall) no LUM image shall be recorded because it does not generate an actionable result.

In the case where the LUM Imaging System indicates that a therapeutic shave needs to be removed but the surgeon decides not to follow this guidance, the reason for not doing so will be recorded in the patient's CRF or during imaging. These instances are considered as a protocol deviation. There are other cases when the shavings reach protocol limits so no shaving will be performed. In these cases, the data will be included in the performance evaluation as is - that is no Luminicell-guided shave-taken will be considered as no removing of cancer or positive margin. However, they will be considered as a detection if there are cancer in the re-excision or if there are positive margins on the corresponding orientations.

Occasionally, a cavity image may be recorded from an unintended region or the image may be deemed as low quality (blurry, out of focus, etc.). For example, the surgeon realizes that he/she placed the device in the wrong location within the cavity after recording an image. Since the LUM software does not allow to overwrite saved images, this situation will be documented, the image will be labeled as "image retaken", "eval", "initialscan" or "transient" and the image will be excluded from the analysis. In addition, images labeled as "lens issue" will be considered as a device malfunction and will be excluded from the analysis.

Other cases are handled as follows:

- When a patient was prescribed Letrozole adjuvant therapy prior to surgery, the patient will be removed from the device performance evaluation.
- When the time from injection of LUM015 to lumpectomy incision is greater than 6 hours due to unplanned surgical delays, the patients will be removed from the device performance evaluation.
- For the re-excision rate endpoints, all patients undergoing a re-excision will be included in the analysis.
- When an image is indicated negative by LUM Imaging System but the shave is taken due to X-ray or pathology suggestion, it will be kept for sensitivity and specificity evaluation, however, for the analysis related to margins, it is conditional and described in g.

LUMICELL CONFIDENTIAL

This document is confidential. Do not disclose or use except as authorized.

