- e. In the case of a therapeutic shave taken but no image saved before the shave was removed, the shave will be excluded from analysis.
- f. In the case of the subject with minor deviation, like no blood drawn, high blood pressure, etc., data will be kept for device performance evaluation.
- g. In the case of SOC shave is taken after use of the Luminicell imaging system, if there is an image for this shave, it will be kept for sensitivity and specificity analysis. If there is a therapeutic shave ahead of the SOC shave but the orientation of the SOC shave is not the same as that of the therapeutic shave taken before it, this SOC shave will be kept for the margin analysis. If the orientation of the SOC shave is same as that of the therapeutic shave taken before it, this SOC shave should be removed from the margin analysis. If there is no therapeutic shave ahead of the SOC shave, this deviated SOC shave will be kept as SOC shave for margin analysis.
- h. In the case of a patient having bilateral lumpectomy, only the data collected from the trial side will be included in the device performance evaluation.
- i. In the case of multiple reports margins and tumors for one block of shave, the distance of the closest margin will be used and ‘Yes’ for the shave containing tumor if at least one report for that block is ‘Yes’.
- j. In the case of the unknown dimension of the shaves or 999 for any of the dimensions, the volume of the shave is the average of that of all the existing shaves of the corresponding type (SOC or Therapeutic).
- k. In the case of a tissue has unknown or unreported distances to margins, the data in the eCRF will indicate “unknown”, it will be interpreted as no specified distance has been reported or the options in the eCRF do not fit the distance description in the pathology report and/or the pathology worksheet. However, the determination for positive or negative margins in the corresponding orientations will depend the pathology determination on whether margins are positive or negative. For example, a pathology report may state “closest margin to invasive cancer is 1mm in medial”. Thus it is assumed that the margins for the other orientations are > 1mm but the specific distance is not reported. For orientations other than medial, the eCRF may indicate “unknown” for margin distance, but the margin status will be considered as “negative” for data analysis.

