- l. For reported microinvasive cancer, adjudicated correction will be provided external to the eCRF and will be used to change the margin type from Invasive to DCIS following NCCN guidelines.
- m. Margins for SOC and final margins will be derived from the tumor distance to margins. If there is a discrepancy between the derived margins based on distance and the margin status determined by the clinical site (could be due to different criteria used by the clinical sites), adjudication of the margin status will be done by Luminicell based protocol defined margin criteria (section 3.1).

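### SAP 4.8.4 sets the margins of orientations with too little tissue to negative whatever pathology found, so a patient with a remaining positive margin can count as converted in the SAP 3.4 proportion

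*SAP*

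**What the plan says.** SAP 4.8.4 describes a list of orientations, by subject, where "there is not enough tissue left for further imaging or removing a therapeutic shave". Its rule is: "The margins of these orientations in the list will be ignored and will be treated as negative margin from the efficacy analyses". Shortage of tissue is the only criterion for listing.

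Elsewhere margin status comes from pathology:

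- SAP 3.1 and Protocol 5.2.1 define a positive margin by tumor on ink, or by DCIS within 2 mm.
- SAP 4.8.3(m) covers both stages: "Margins for SOC and final margins will be derived from the tumor distance to margins".
- Protocol 5.4.3 takes the final margin from the outermost resected surface of each orientation.
- Protocol Table 1 and 5.3 explain why an anterior or posterior shave may be omitted, but do not call such a margin negative.

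SAP 3.4 has two proportions whose denominator is the patients with a positive margin after SOC. The first counts those with a LUM signal above threshold. The second, the conversion proportion, is worded as pathology-positive patients made pathology-negative by therapeutic shaves. Its formula asks only that all final margins be negative.

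SAP 4.8.3 has a neighbouring rule for cases where the system "indicates that a therapeutic shave needs to be removed but the surgeon decides not to follow this guidance", or where the shave limit is reached. There, "no Luminicell-guided shave-taken will be considered as no removing of cancer or positive margin", and the case counts as a detection if the re-excision contains cancer or "if there are positive margins on the corresponding orientations".

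**The concern.** A positive margin does not become negative because no more tissue can be taken. SAP 3.4 presents the conversion proportion as an indication of how many re-excisions the system could spare. A margin that pathology called positive, and that no therapeutic shave removed, should not add to that figure. SAP 4.8.3(c) keeps every re-excised patient in the re-excision rate endpoints, so one patient could be reported both as converted and as re-excised for the same remaining margin.

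Because no stage is named, two analysts could also follow 4.8.4 in good faith and report different proportions. SAP 3.4 labels these analyses as secondary endpoints of the pivotal study, which is a further reason to settle the definition here.

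**Working it through.** **No planned figure to reproduce.** No number in either document depends on 4.8.4. The expected 67 patients in Protocol 15.2 reproduces as 32/(19/40) = 67.4, and serves below only as a possible study size.

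**Classification.** Take four kinds of patient who are pathology-positive after SOC:

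- A: her only positive margin is listed and unshaved.
- B: therapeutic shaves cleared her other positive margins, but a listed margin stays positive.
- C: as B, but an unlisted margin also stays positive.
- D: a true converter whose only positive orientation was listed, for example because little tissue was left after the shave.

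Each cell gives (in denominator, counted as converted) under the SAP 3.4 formula.

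| Type | Pathology status | SOC-only recode | Final-only recode | Both-stage recode |
|---|---|---|---|---|
| A | yes, no | no, no | yes, yes* | no, no |
| B | yes, no | yes, no | yes, yes | yes, yes |
| C | yes, no | yes, no | yes, no | yes, no |
| D | yes, yes | no, no | yes, yes | no, no |

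*Only by the formula. The endpoint's wording about therapeutic shaves would exclude her if she had none.

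Type B is the firm case: she had therapeutic shaves, still has a pathology-positive margin, and counts as converted under two of the three recodes.

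**Effect on the proportion.** Let D be the patients positive after SOC, c the true converters and k the affected patients.

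- Pathology status: c/D.
- Type B (final-only or both-stage), or type A (final-only, by the formula): (c + k)/D, a rise of 1/D per patient.
- Type A, both-stage: c/(D − k).
- One type D patient, both-stage: (c − 1)/(D − 1), a fall.

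**Range for D.** Protocol 3.1 gives 17% to 59% for close or positive margins, and Protocol 15.2 gives 67 expected and 250 maximum patients. Then 0.17 × 67 = 11.4, taken as 11, and 0.59 × 250 = 147.5, taken as 147. So 1/D runs from 1/11 = 9.1 points to 1/147 = 0.7 points.

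**Illustration.** All counts are assumed. Protocol 3.1's general figure of about a third needing further surgery gives 67/3 = 22.3, taken as 22, and 250/3 = 83.3, taken as 83. True conversion is set at 7/22 and 25/83.

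| | D = 22 | D = 83 |
|---|---|---|
| Pathology status | 7/22 = 31.8% | 25/83 = 30.1% |
| (c + k)/D, k = 1 | 8/22 = 36.4% | 26/83 = 31.3% |
| (c + k)/D, k = 2 | 9/22 = 40.9% | 27/83 = 32.5% |
| Type A, both-stage, k = 1 | 7/21 = 33.3% | 25/82 = 30.5% |
| Type A, both-stage, k = 2 | 7/20 = 35.0% | 25/81 = 30.9% |
| One type D, both-stage | 6/21 = 28.6% | 24/82 = 29.3% |

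**The first SAP 3.4 proportion** shares the denominator and can move either way. From an assumed 16/22 = 72.7%, dropping two type A patients gives 16/20 = 80.0% if neither had a LUM signal, or 14/20 = 70.0% if both did.

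**The 2x2 table.** SAP 3.3.2 uses the margin as truth standard only when there is neither a shave nor a re-excision. Where tissue is too thin to act on, SAP 4.8.3 says "no LUM image shall be recorded because it does not generate an actionable result". Few listed orientations should therefore reach the table. The documents give no base for a figure.

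**Against the 4.8.3 rule.** The two rules meet only where a LUM-indicated shave was not taken because tissue was lacking. There 4.8.3 gives no credit for removal, and counts a detection if the margin is positive, while 4.8.4 calls the same margin negative.

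**The case against.** The best defence is that 4.8.4 is a specific, pre-stated exception to general rules. It says the margins are ignored and names no stage, so its natural reading is that listed orientations are set aside throughout. For the SAP 3.4 proportions this is identical to a both-stage recode: a patient is positive if any orientation is positive, and converted if all are negative. The question would then be which estimand comes first, since the system cannot guide a shave where none can be taken.

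Much of this stands. Setting listed orientations aside is a legitimate supplementary target. It is not the endpoint that SAP 3.4 describes in pathology terms, and under it type B is still reported as converted with a pathology-positive margin in place.

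A reader might infer more than the documents support:

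- *Any unshaved positive margin counts as a success.* A patient whose only positive margin is listed counts as converted only under a final-only recode that follows the formula and disregards the endpoint's wording about shaves.
- *The rule always flatters the device.* Type D lowers the proportion, and an SOC-only recode leaves type B unconverted.
- *4.8.4 and 4.8.3 conflict generally.* They do so only in the narrow case above.

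**Conclusion.** The point stands in this limited form. SAP 4.8.4 lets a shortage of tissue override pathology in an endpoint defined by pathology, and leaves the stage unstated. The firm consequence is type B. Removal of type A from the denominator depends on SOC margins being recoded too. The conversion proportion usually rises or is unchanged, but can fall.

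The size cannot be derived, because neither document counts listed orientations or those that were pathology-positive. The range of about 9 to 0.7 points per patient counted as converted assumes that Protocol 3.1's background rates for close or positive margins apply here. The illustrated proportions rest on assumed counts throughout.

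Phase C has no hypothesis-tested endpoints, and these proportions are descriptive and secondary. The residual-cancer metric in SAP 3.2 does not use margins, the re-excision rate endpoints are unaffected, and any effect on sensitivity and specificity is limited. This should be fixed, but it does not threaten the study's main results.

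**What to change.** Replace the rule in SAP 4.8.4 with:

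> *For the 3.4 margin proportions, listed orientations keep their pathology margin status (3.1, with adjudication under 4.8.3 m) at both the SOC and the final stage, with 4.8.3 g applied at both stages. A listed orientation that is still positive counts as not converted. The same proportions with listed orientations set aside at both stages are reported as a supplementary analysis, with the numbers of listed and of pathology-positive listed orientations. Listed orientations that were imaged keep the 3.3.2 truth standard.*

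The reference to 4.8.3(g) must cover both stages. For an SOC shave taken after a therapeutic shave in the same orientation, that item says "this SOC shave should be removed from the margin analysis". Otherwise such a shave could define the final margin as the outermost surface.

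The new text also reconciles 4.8.4 with 4.8.3, because an indicated shave not taken for lack of tissue is then judged on the pathology margin under both.

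The cost is a short SAP edit and one extra table, from pathology data and a list that the SAP already relies on. The conversion proportion may come out less favourable.

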4.9 Exploratory data

Exploratory analysis of the types of tissue found in the therapeutic shaves is based on “free text” entered in the eCRF.

5 References

1. Moran, M.S., et al., *Society of Surgical Oncology-American Society for Radiation Oncology consensus guideline on margins for breast-conserving surgery with whole-breast irradiation in stages I and II invasive breast cancer*. Int J Radiat Oncol Biol Phys, 2014. **88**(3): p. 553-64.
2. Morrow, M., et al., *Society of Surgical Oncology-American Society for Radiation Oncology-American Society of Clinical Oncology Consensus Guideline on Margins for Breast-Conserving Surgery With Whole-Breast Irradiation in Ductal Carcinoma In Situ*. J Clin Oncol, 2016.

LUMICELL CONFIDENTIAL

This document is confidential. Do not disclose or use except as authorized.
